### Sensitivity analysis to Primary analysis

A sensitivity analysis will replace the factorial models with multiarm models, in which the assumption of no interaction between treatments is relaxed.(49)

Further sensitivity analyses may explore alternatives to the proportional odds model (such as the Generalized Ordered Logit/Partial Proportional Odds Model or multinomial logistic regression) for the primary outcome.

### Analysis of secondary outcomes

Outcomes expressed as incidences or incidence rates will be examined using a suitable mixed effects regression model such as logistic, Poisson or negative binomial.

Outcomes where it is important to account for competing events such as death, or where the interest is in the timing or duration of the event, will be analysed as time-to-event or time-to-recovery data as appropriate, using sub-distribution hazard models(50) to account for the dependent competing risk of censoring when subjects transition to a less favourable clinical state (e.g. death).

All serious adverse events will be tabulated by arm and severity, displaying the number of participants with at least one adverse event and the number of adverse events. We will also calculate odds ratios and incidence rate ratios and their 95% CIs for binary and count SAE outcomes (including 1-year mortality) at SOC level using mixed effects logistic regression and Poisson, negative Binomial model or similar models for count data as appropriate.

Antibiotic use, quality of Life (EQ-5D-5L) and cognitive function (MoCA-Blind) will be summarised by arm (mean, standard deviation and 95% CI) and analysed using univariate linear mixed models.

All models used to analyse secondary outcomes will include the same adjusting variables as the corresponding primary analyses.

A detailed statistical analysis plan will be written prior to first data extraction from the database and will detail all analysis models and model checks to be performed.

Sponsor: Imperial College London

Version 1.1 22-Aug-2023

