# **Secondary Endpoints**

- Duration of mechanical ventilation, vasopressor use, renal replacement therapy during index hospital admission up to 90 days
- Length of stay in ICU and hospital up to 90 days
- Antibiotic use (defined daily doses per 1000 occupied bed days and antibiotic-free days) during index hospital admission up to 28 days
- Infection relapse / recurrence or secondary infection requiring further antibiotic treatment during index hospital admission up to 28 days
- Adverse events and adverse drug reactions (including antibiotic related adverse events) during index hospital admission up to 28 days
- Health-related Quality of Life (EQ-5D-5L) and cognitive function (MoCA-Blind) at 6 months
- 1-year mortality
- Incremental costs per Quality-Adjusted Life Year (QALY), and Incremental Net monetary Benefits (INB)

Sponsor: Imperial College London

Version 1.1 22-Aug-2023

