#### 9. STATISTICAL ANALYSES

### Sample Size and power considerations

The sample size has been calculated based on 90-day mortality. To increase the power of the trial the primary outcome will include both 90-day mortality and clinical state (in-hospital without organ support, in-ICU with organ support, discharged) over 90 days. Simulations to further examine the power of the study under a range of conservative outcomes on the primary outcome with clinical state included have been performed on the planned trial sample size based on mortality alone.

The initial calculation used data from the ICNARC Case Mix Programme which reported a mortality rate of 31.8% for all sepsis admissions to ICU.(43) Allowing for the trial exclusion criteria we anticipate a 30% mortality rate in the standard of care arm.

In the diagnostic and fluid trials we aim to recruit 3758 patients to both trials. This is based on a clinically important target difference in mortality of 5%. Assuming 30% mortality, 5% reduction, 90% power, 5% two-sided type I error we will require 1674 per arm. We then inflate by 10% for a potential interaction effect between the intervention arms, and 2% to account for loss to follow-up.

The high-risk subset (35% eligibility for GM-CSF) will have a higher control mortality rate.(43-45) We assume a 45% mortality rate in the standard of care arm. Our meta-analysis for GM-CSF in sepsis trials demonstrated a relative risk for mortality of 0.74 (95%CI 0.49-1.14). We aim to recruit 1300 participants which will provide 90% power to detect 9% difference in mortality with type I two-sided error or 5%, and factoring in approximately 2% loss to follow up.

No adjustments for multiple comparisons have been made for these three trials as the comparisons are three distinct treatments where each result will provide a separate conclusion. (46)

In addition, we have undertaken simulations to further examine the power of the primary analysis of 90-day mortality and clinical states (in-hospital without organ support, in-hospital with organ support, discharged) for the antibiotic and fluid trials, assuming a more conservative reduction in mortality. Treating clinical state as an ordinal outcome which is repeatably observed over time increases statistical efficacy because it makes the most of all the information available. We define clinical status as an ordinal outcome with three passing states and one absorbing state.

Clinical status is categorised as:

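### DDD per 1000 occupied bed days is defined as a bed-day rate, but the mean/SD summary and linear mixed model fixed for it would report an average of patient ratios

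*Protocol*

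**What the plan says.** The list of secondary endpoints (section 3, repeated in the Trial Summary) puts two measures under one heading: "Antibiotic use (defined daily doses per 1000 occupied bed days and antibiotic-free days) during index hospital admission up to 28 days". The first is a consumption rate with a bed-day denominator; the second is a count of days per patient.

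Under Analysis of secondary outcomes (section 9) the two are not separated: "Antibiotic use, quality of Life (EQ-5D-5L) and cognitive function (MoCA-Blind) will be summarised by arm (mean, standard deviation and 95% CI) and analysed using". The sentence goes on to name a linear mixed model for all of them. Nothing says how bed days enter, whether as denominator, weight or offset.

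The same subsection opens with a general rule: "Outcomes expressed as incidences or incidence rates will be examined using a suitable mixed effects regression model such as logistic, Poisson or negative binomial". It closes by saying that the statistical analysis plan "will detail all analysis models and model checks to be performed".

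**The concern.** A mean, an SD and a linear mixed model all operate on one value per patient. For the DDD measure, that value can only be the patient's DDD divided by that patient's own bed days. Each ratio then counts equally, whether it rests on 1 bed day or 28. The endpoint as named is total doses over total bed days, in which each patient counts in proportion to bed days. The two agree only when the patient ratio is uncorrelated with length of stay. Antibiotic courses are finite, so a long stay usually contains untreated days and a lower ratio.

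Antibiotic stewardship is part of the diagnostic trial's question in the Trial Summary, and this is one of two antibiotic-use measures. Arm figures labelled in the endpoint's unit but computed as patient averages would not be that quantity, and could not be set beside figures formed as total doses over total bed days.

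**Working it through.** **What the protocol supplies.** It states no DDD rate, SD, course length or target difference for antibiotic use, so there is no figure of its own to reproduce for this endpoint. The trial size, used only to set the scale, does reproduce. For 30% against 25%, 90% power and two-sided 5%: n = [1.960 × √(2 × 0.275 × 0.725) + 1.282 × √(0.30 × 0.70 + 0.25 × 0.75)]² / 0.05² ≈ 1674 per arm. Then 2 × 1674 × 1.10 / 0.98 = 3757.96, that is 3758, or 1879 per arm.

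**Identity.** Let Dᵢ be a patient's DDD, Lᵢ the bed days and rᵢ = Dᵢ/Lᵢ. The endpoint's rate is ΣDᵢ/ΣLᵢ, which is the mean of rᵢ weighted by Lᵢ. Hence

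mean(r) − ΣD/ΣL = −cov(r, L) / mean(L).

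If the ratio falls as stay lengthens, the covariance is negative and the patient average exceeds the rate.

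**Two-patient example** (assumed 1.5 DDD per treated day):
- Patient 1: 3 treated days in a 3-day stay. 4.5 DDD / 3 days = 1500 per 1000 bed days.
- Patient 2: 7 treated days in a 28-day stay. 10.5 / 28 = 375 per 1000.
- Patient average: (1500 + 375)/2 = 937.5.
- Rate: 1000 × 15/31 = 483.9.
- Check: cov = [(562.5)(−12.5) + (−562.5)(12.5)]/2 = −7031.25, mean stay 15.5, and 7031.25/15.5 = 453.6 = 937.5 − 483.9.

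**Illustration with the protocol's own stay pattern.** Table 2 gives the share still in hospital (1 − discharged − dead) as 1, 0.89, 0.61 and 0.31 at days 0, 7, 14 and 28. Stay was drawn from this, linear between points and capped at 28 days. Assumptions not in the protocol: mean 2 DDD per treated day; course length gamma with SD half its mean, cut off at the end of stay; 10 to 30% of intervention patients stopped at day 3.

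With course length independent of stay, control-arm values are:

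| Mean course | Mean of patient ratios | Total DDD / total bed days × 1000 | Excess |
|---|---|---|---|
| 6 days | about 806 | 607 | 33% |
| 8 days | about 994 | 785 | 27% |
| 12 days | about 1280 | 1087 | 18% |

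If course length is partly correlated with stay, the excess is about 10 to 18%. If treated days are a fraction of stay unrelated to its length, both figures are about 1200 and the excess is zero. A separate set-up (log-normal stay with median 12 days, courses of about 7 days) gives 902 against 689, a 31% excess.

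**Between-arm ratio.** Patient-ratio against bed-day version, in different scenarios: 0.950 against 0.950, 0.970 against 0.960, 1.055 against 1.053, 0.893 against 0.879, 0.84 against 0.82. The largest shift seen is about 0.03.

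**Precision.** Efficiency of the linear analysis relative to the bed-day version (ratio of squared z):
- Finite courses, independent of or partly correlated with stay: about 0.57 to 0.91.
- Treated days proportional to stay: about 0.93 to 0.96.
- Counts varying about an underlying patient rate unrelated to stay: 1/1.52 = 0.66 when all patients share one rate, but 1/0.99 = 1.01, 1/0.87 = 1.15, 1/0.83 = 1.20 and 1/0.80 = 1.25 as patients differ more (gamma shape 10, 4, 2, 1).

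The direction therefore changes with assumptions that the protocol does not settle.

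**The case against.** Four points can be made for the protocol.

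- **The statistical analysis plan will give the detail, and the protocol never says per patient.** True, and how a ratio is formed is ordinary content for that plan. But the protocol does not leave the matter open: it names the summary and the model, and neither produces the rate in the endpoint list without something further. This answers the charge of a missing detail but does not remove the mismatch.
- **A linear model on patient ratios is a valid randomised comparison.** It is. It compares mean patient-level antibiotic density, and equal weighting is a legitimate choice of estimand. Bed days are also a post-randomisation outcome, so weighting by them is not automatically better. What stands against it is the label: the endpoint names the other quantity.
- **The subsection does not contradict itself.** A reader might infer that it does, because the opening rule sends rates to count models. The documents do not support this. The rule covers incidences and incidence rates and gives its models as examples. DDD is a non-integer amount of drug rather than a count of events, and the later sentence on antibiotic use can be read as a specific exception.
- **The treatment comparison hardly moves.** This also stands. The distortion is mainly in the arm-level figures.

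**Conclusion.** The concern holds as a mismatch between one secondary measure and its stated analysis. Read as written, the arm figures would be means of patient ratios rather than DDD per 1000 occupied bed days. Under finite courses averaging 6 to 12 days, the excess is illustratively 10 to 33%; it vanishes if treated days scale with stay. These figures rest on assumed course lengths and dose intensity, with only the stay pattern taken from the protocol.

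A reader might go further and infer that the linear model wastes a fixed share of the sample. That is not supported: the protocol gives no variance, rate or course length, and the efficiency comparison runs from a clear loss to a gain for the linear model. No general loss of precision is claimed.

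Severity is minor. The primary analysis, the sample size and the analysis of antibiotic-free days are unaffected.

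**What to change.** Under Analysis of secondary outcomes, take the DDD measure out of the linear-model sentence and state instead:
- each arm's rate is total DDD divided by total occupied bed days to day 28, times 1000, with a confidence interval;
- arms are compared with a log-link model of each patient's total DDD, with log(occupied bed days) as offset, robust or overdispersed variance, and the same covariates as the other secondary models.

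Keep the linear mixed model for antibiotic-free days, EQ-5D-5L and MoCA-Blind. A mean of patient ratios may stay as a supplementary summary if labelled as such.

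The cost is a sentence or two in the protocol, carried into the statistical analysis plan, and no new data. The effect becomes a rate ratio instead of a mean difference. Because bed days may themselves respond to treatment, the rate ratio should be read beside length of stay and antibiotic-free days.

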#### 10. ECONOMIC EVALUATION

#### Overview

We will undertake a full health economic evaluation for each of the three comparisons. Each evaluation will follow NICE methodological guidance in taking an NHS and personal social services perspective.(51) The interventions are: rapid PCR-based microbiological diagnostics combined with procalcitonin; conservative fluid therapy with de-resuscitation; and the use of GM-CSF in high-risk patients. We will estimate the incremental quality-adjusted life year (QALYs) and costs of each intervention compared to 'usual' care. We will report cost-effectiveness metrics, including the incremental costs per QALY and the incremental net monetary benefits (INB). We will calculate the INB by valuing any differences in mean quality-adjusted life year (QALY) between the comparison groups, at NICE recommended thresholds (e.g. £20,000 per QALY) and subtracting the incremental cost. The economic evaluation will proceed in two phases. In the first phase, we will undertake a 'trial-based' evaluation which directly uses information from each randomised comparison, but with the time horizon limited to the end of trial-follow-up (one year). In phase two we will use a model to extend the trial-based evaluation to report cost-effectiveness over the lifetime.(51) For both phases we will report the incremental costs, QALYs and INB of each intervention versus usual care

#### **Trial-based evaluations**

Each economic evaluation will extract patient-level information on resource use, in particular the length of stay in critical care, according to levels of organ support, and the overall length of hospital stay. We will collate this information from the ICNARC CMP database, for the index hospital admission and also any readmissions up to one year. We will combine information from hospital resource use including using levels of organ support to categorise, Healthcare Resource Group within critical care, with unit costs from the 'Payment by Results' database, to report total hospital costs up to one year.(52) The use of personal health services will be recorded by patient questionnaire at six months, and valued with unit costs from the Personal Social Services Research Unit (www.pssru.ac.uk).

We will combine responses to the EQ-5D-5L questionnaire at 90 days, with the NICE recommended approach to valuing EQ-5D-5L at the time of analysis, to report mean HRQoL for each randomised arm. We will calculate QALYs at one year by combining the HRQoL with survival time, and will previous research in sepsis in assuming that the individual's HRQoL reported 90 days is maintained at 12 months.(53)

For each of the three evaluations we will report the incremental QALYs, costs and INB over one year for each intervention versus usual care, overall, and according to the same pre-defined subgroups as for the evaluation of clinical effectiveness. We will extend the analytical approach taken in the main statistical analysis to allow for additional issues raised by the health economic evaluation, in particular those of multiple outcomes (costs and QALYs), and that these endpoints tend to have skewed distributions. The sensitivity analysis will test whether the results are robust to methodological assumptions, for example: the assumption that HRQoL at 90 days is maintained until 12 months, alternative assumptions about the unit costs (e.g. for sargramostim), and different cost-effectiveness thresholds (e.g £10,000, £30,000 per QALY).

Sponsor: Imperial College London

Version 1.1 22-Aug-2023

### Health economic modelling

We will develop mathematical models that use the trial-based estimates in capturing the long-term consequences of the interventions compared to usual care, according to avoided mortality or morbidity or cost differences. Decision-analysis modelling will be used to estimate the expected costs incurred and patient outcomes over the lifetime. The model will be constructed in line with latest NICE recommendations.(51) The above estimates from the study, together with measures of uncertainty will be used to populate the model. Key input parameters will include the underlying risk of mortality and morbidity associated with current care and the treatment effect sizes associated with combinations of interventions to estimate the health status of patients at defined time points, and the costs associated with care in hospital.

The model will extrapolate beyond the end of the study to estimate the QALYs conditional on the proportion of patients who are alive, and of these, the proportion that would have reduced health-related quality of life in the future. Estimates of long-term survival rates (which may be reduced due to prior sepsis) and of the disutility associated with observed adverse events in the study will be sourced from peer-reviewed literature. Similarly, any costs associated with long-term disabilities will be identified and included within the decision-analysis model.

The mathematical model will allow an explicit evaluation of the uncertainty in any conclusions drawn from the trial and allow value of information analyses to be performed to indicate if further research would be deemed as value for money. At present the precise modelling methodology to be implemented has not been determined. This decision will be made in conjunction with clinical experts and having assessed the available data.

### 11. REGULATORY, ETHICAL AND LEGAL ISSUES

### **Declaration of Helsinki**

The investigator will ensure that this study is conducted in full conformity with the 2013 revision of the 1964 Declaration of Helsinki.

#### **Good Clinical Practice**

The study will be conducted in accordance with the guidelines laid down by the International Conference on Harmonisation for Good Clinical Practice (ICH GCP E6 guidelines).

## Research Ethics Committee (REC) Approval

### **Initial Approval**

Prior to the shipment of the IMP and the enrolment of participants, the REC must provide written approval of the conduct of the study at named sites, the protocol and any amendments, the Participant Information Sheet and Consent Form, any other written information that will be provided to the participants, any advertisements that will be used and details of any participant compensation.

## **Approval of Amendments**

Proposed amendments to the protocol and aforementioned documents must be submitted to the REC for approval. Amendments requiring REC approval may be implemented only after a copy of the REC's approval letter has been obtained.

Sponsor: Imperial College London

Version 1.1 22-Aug-2023

Amendments that are intended to eliminate an apparent immediate hazard to participants may be implemented prior to receiving Sponsor or REC approval. However, in this case, approval must be obtained as soon as possible after implementation.

Amendments to the protocol will be decided by the Chief Investigator and the Protocol Development Group and will be submitted to the Imperial College London Research Governance and Integrity Team for review prior to submission. Whether the changes in the protocol are substantial or non-substantial will be guided by the amendment tool as provided by the HRA/REC. An updated version and date of the protocol will be documented in the title and footer of the document, the approval pack (containing the updated protocol) will also be sent to all participating sites.

### **Annual Progress Reports**

Annual Progress Reports will be submitted to the Research Ethics Committee (REC) and the Sponsor in accordance with local / national requirements. The Annual Progress Report will also detail all SAEs recorded.

#### **End of Trial Notification**

The REC will be informed about the end of the trial, within the required timelines.

The end of trial notification will be submitted within 90 days of the end of trial definition being met. In the event of a premature halt of the trial, the timeframe is 15 days, and the reasons should be clearly explained in the notification.

### **Regulatory Authority Approval**

The study will be performed in compliance with UK regulatory requirements. Clinical Trial Authorisation from the Medicines and Healthcare products Regulatory Authority (MHRA) must be obtained prior to the start of the study. In addition, the REC/MHRA must approve amendments prior to their implementation (as instructed by the Sponsor), receive SUSAR reports and annual safety updates, and be notified of the end of the trial.

This study has Clinical Trials Authorisation from the UK Competent Authority; MHRA. Reference: IRAS 1005848

#### HRA approval

Health Research Authority (HRA) approval will be obtained prior to starting the study. Each participating site will confirm capacity and capability prior to commencing.

The HRA and all participating sites also need to be notified of all protocol amendments to assess whether the amendment affects the institutional approval for each site.

### **Non-Compliance and Serious Breaches**

All protocol deviations and protocol violations will be reported via the eCRF/CRF and reviewed by the Chief Investigator and reported to the ICTU Head of QA on a monthly basis. Protocol violations will be reported to the Sponsor.

An assessment of whether the protocol deviation/violation constitutes a serious breach will be made.

A serious breach is defined as:

Sponsor: Imperial College London

Version 1.1 22-Aug-2023

A breach of the conditions and principles of GCP in connection with a trial or the trial protocol, which is likely to affect to a significant degree:

- The safety or physical or mental integrity of the UK trial participants; or
- The overall scientific value of the trial

The Sponsor will be notified within 24 hours of identifying a likely Serious Breach. If a decision is made that the incident constitutes a Serious Breach, this will be reported to the MHRA and REC within 7 days of becoming aware of the serious breach.

### **Insurance and Indemnity and Sponsor**

The Sponsor has civil liability insurance, which covers this study in all participating countries. Imperial College London holds negligent harm and non-negligent harm insurance policies which apply to this study.

Imperial College London will act as the main Sponsor for this trial. Delegated responsibilities will be assigned to the NHS trusts taking part in the trial.

